6.1.4 Treatment duration

The planned duration of study treatment is 48 weeks. Participants may be discontinued from treatment earlier (see [Section 9.1.1](#)).

6.2 Other treatment(s)

Participants experiencing disease signs and symptoms may receive short-term symptomatic care with over-the-counter, anti-inflammatory/analgesic agents such as nonsteroidal anti-inflammatory drugs (NSAID) and paracetamol. Participants whose SjS disease signs and symptoms are not adequately controlled by symptomatic care, and/or who suffer from more severe SjS disease manifestations not suitable for such treatment, may receive rescue therapy with corticosteroids, if determined by the Investigator to be medically necessary ([Section 6.2.3](#)).

There is currently no consensus on the definition of flare in SjS. With reference to the recently completed JOQUER trial in pSS ([Gottenberg et al 2014](#)) that reported 12 flares among 120 patients during 12 months, it is conceivable that < 10% of all patients in the current iscalimab trial will experience a deterioration (or ‘flare’) that warrants treatment escalation. Treatment escalation would, for example, be increasing the steroid dose, or introducing de novo an immunosuppressant agent like azathioprine. Participants who require escape treatment (other than allowed rescue medications – see [Section 6.2.3](#)) must be discontinued from study medication, enter the safety follow-up period and follow the local standards for treatment of SjS worsening. In the absence of consensus guidelines for treatment of systemic manifestations in SjS, it is recommended to consult the SLE treatment guidelines as far as they pertain to the respective organ involvement observed in the trial (for example renal, nervous system or skin vasculitis).

Any medication used to treat Adverse Events (AE) must be recorded on the Case Report Form (CRF).

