6.2.2 Prohibited medication

Use of treatments displayed in the below table is not allowed in study periods as indicated.

Table 6-2 Prohibited medication

Medication	Prohibited in Study Period	Action to be taken
Other experimental therapies	All	Study treatment discontinuation required, participants should remain in the study and follow visit schedule
Other biologics (for treatment of autoimmune diseases e.g., SjS, SLE, RA)	All	Study treatment discontinuation required, participants should remain in study and follow visit schedule

Medication	Prohibited in Study Period	Action to be taken
DMARDs or other immune suppressive agents or changes in an existing DMARD regimen (hydroxychloroquine, methotrexate, azathioprine)	Treatment period	Study treatment discontinuation may be required on a case-by-case basis
Prednisone >10 mg (or equivalent other corticosteroid)	Treatment period	Study treatment discontinuation may be required on a case-by-case basis
Intravenous or oral cyclophosphamide; oral cyclosporine; oral MMF	All	Study treatment discontinuation required, participants should remain in the study and follow visit schedule
Existing co-medications observed to cause in an individual patient a major side effect of dry mouth/eyes. Examples include antihistamines, antidepressants, anticholinergics, sedatives, antipsychotic drugs, anti-Parkinson agents A comprehensive guide to medications with documented effects on salivary gland function or symptoms has been published by Wolff et al 2017 (please see the footnote).	Treatment period	Study treatment discontinuation may be required on a case-by-case basis
Live/attenuated vaccine	During treatment and for at least 14 weeks thereafter	Study treatment discontinuation required, participants should remain in the study and follow visit schedule

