^X Assessment to be recorded in the clinical database or received electronically from a vendor

¹ Corresponds to the Week 60 visit of the core study. Assessments carried out as part of Week 60 as per core study protocol should be used for Week 60E1 of the extension study.

² Optional site visits - Week 66, 70, 74, 78, 82, 86, 90, 94, 98, 102, 106. Participants who are unable to self-administer the PFS injections at home will visit the site and site staff will supervise self-administration or administer the PFS injection for them. Other participants who can self-administer the PFS injection can do so at home at these optional visits.

³ Informed consent should be obtained before commencement of the Week 60 assessments of the core study.

⁴ Contact IRT for new treatment reassignment.

⁵ AEs/SAEs occurring after the participant has signed the informed consent must be captured on the appropriate eCRF page.

⁶ C - These assessments shall be conducted as part of the core study CCFZ533B2201 and will not be repeated in this extension study

⁷ S - Assessment to be recorded in the source documentation only

⁸ [REDACTED]

⁹ Local lab testing of CMV IgG, IgM and DNA (by PCR) must be performed every 3 months until end of study. Hepatitis B monitoring applicable to HBsAg (-) patients who were HBcAb (+) and HBV DNA (-) at screening during the core study. Local lab testing of HBsAg and HBV DNA must be performed every 3 months until end of study.

¹⁰ While on treatment, coagulation monitoring applies only to participants who have antiphospholipid antibodies (lupus anticoagulant, anti-cardiolipin antibodies) and/or who are on pre-existing antithrombotic therapy/prophylaxis, as reflected in the exclusion criteria of the TWINSS core study protocol.

¹¹ Analysis of cryoglobulins will be done only for participants who were positive at screening in the TWINSS core study.

¹² Urine pregnancy tests will be performed throughout the study

¹³ Blood sample is collected pre-dose.

¹⁴ [REDACTED]

¹⁵ [REDACTED]

¹⁶ Optional [REDACTED]

¹⁷ [REDACTED]

¹⁸ [REDACTED]

¹⁹ In case of premature discontinuation, participants will enter the follow-up after completing assessments for this visit.

²⁰ Mandatory to all participants, including those who have discontinued the study prematurely.

²¹ Week 106 is the last dose administration visit in the Treatment Period.

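### A new immunosuppressant for a flare is a mandatory stop of study drug in Protocol 6.2 but case by case in Table 6-2, and the visit path after stopping is unclear

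*Protocol*

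**What the plan says.** **Protocol 6.2.** On flares: "Treatment escalation would, for example, be increasing the steroid dose, or introducing de novo an immunosuppressant agent like azathioprine". The next sentence sets the consequence. It opens "Participants who require escape treatment (other than allowed rescue medications", points to Section 6.2.3 for that exception, and continues that such participants "must be discontinued from study medication, enter the safety follow-up period and follow the local standards for treatment of SjS worsening".

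**Protocol 6.2.2, Table 6-2.** One row covers "DMARDs or other immune suppressive agents or changes in an existing DMARD regimen (hydroxychloroquine, methotrexate, azathioprine" and is prohibited in the treatment period. Its action is "Study treatment discontinuation may be required on a case-by-case basis". Prednisone above 10 mg carries the same action. The rows for experimental therapies, for cyclophosphamide, cyclosporine and MMF, and for live vaccines say "Study treatment discontinuation required, participants should remain in the study and follow visit schedule". The row for other biologics says the same in almost identical words.

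**Protocol 6.2.3 and 9.1.1.** Section 6.2.3 tells the investigator to apply the Table 6-2 action when a listed drug is needed as rescue, and it permits corticosteroids for flares. Section 9.1.1 lists prohibited treatment as a ground for stopping, on the terms of the prohibited-medication section.

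**Protocol Table 8-1.** Footnote 19, attached to the Wk 108/TD visit: "In case of premature discontinuation, participants will enter the follow-up after completing assessments for this visit". Footnote 20 makes the Wk 120/EOS visit mandatory for everyone, including early discontinuers.

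**The concern.** An investigator who starts azathioprine for a flare can find two answers on whether iscalimab continues. Safety is the primary objective. Section 4.5 treats infection as an important potential risk and describes a fatal case confounded by concomitant immunosuppressants. Whether someone receives iscalimab together with a new immunosuppressant should not depend on which section the site reads.

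The decision also feeds the analysis. It fixes the last dose date, and hence exposure (SAP 2.3.1) and the end of the treatment-emergent window (SAP 2.4). It also affects who is counted as completing study periods (SAP 2.2.1). The visit path then determines how much off-drug laboratory and vital-sign data are collected, and Protocol 12.4.3 includes all of it regardless of intercurrent events.

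**Working it through.** The plan gives no figure to reproduce. The main check sets the passages side by side. Arithmetic enters only for scale and for the visit windows.

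**1. One event: new azathioprine for a flare during treatment**

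| Place | What happens to study drug |
|---|---|
| 6.2 | Azathioprine is the named example of escalation; escape treatment beyond allowed rescue means a mandatory stop |
| 6.2.3 | Apply the action in Table 6-2 |
| Table 6-2, DMARD/immunosuppressant row | Stopping decided case by case |
| 9.1.1 | Defers to the prohibited-medication section, so case by case |

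The first line does not agree with the other three.

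**2. After stopping**

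| Place | Visit path |
|---|---|
| 6.2 | Safety follow-up |
| Table 8-1, footnotes 19 and 20 | TD visit, then follow-up; Wk 120/EOS for all |
| 9.1.1 | Not withdrawn; return for the follow-up assessments where possible |
| Table 6-2, rows requiring a stop | Remain in study on the visit schedule |
| Table 6-2, case-by-case rows | Silent |

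The visit schedule in the fourth line could mean the TD and follow-up columns, or the remaining treatment-period visits as well. The text does not say.

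**3. Scale**

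- Inputs: the protocol's expectation of fewer than 10% needing escalation (6.2); 160 planned (Protocol 12.8); 206 enrolled (SAP 1.1).
- 10% × 160 = 16, and 10% × 206 = 20.6. These are ceilings for every kind of escalation, steroid increases included.
- No rate is given for new or changed DMARD or immunosuppressant use.

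**4. Visit windows (illustration)**

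- Table 8-1 places Wk 112 at 785 − 757 = 28 days after Wk 108, and Wk 120 at 841 − 757 = 84 days after.
- SAP Table 2-1, for vital signs, hematology and chemistry, runs Week 112 from EoP3 + 1 to Day 393 and starts Week 120 at Day 394.
- Assumptions: EoP3 is the early end-of-treatment date (the SAP does not say how it is set for stoppers); the TD visit falls on Day 85, the Week 72 target; follow-up visits keep their usual spacing.
- The Week 112 window is then Days 86 to 393. Follow-up visits fall on 85 + 28 = Day 113 and 85 + 84 = Day 169.
- Both days lie in the Week 112 window. Day 113 also lies in Week 76 (Days 100–127) and Day 169 in Week 84 (Days 156–183). Neither reaches Week 120.
- The SAP has a rule for several assessments in one window, but none for one assessment in two windows.

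**The case against.** The best defence is that the documents already link up. Section 6.2 exempts allowed rescue and points to 6.2.3, and 6.2.3 points to Table 6-2. On that reading the mandatory stop applies only to the rows where the table itself requires stopping, and azathioprine is case by case throughout. Section 6.2 also uses two terms, escalation and escape treatment, and does not equate them. This reading is coherent, but it has to treat a drug on the prohibited list as allowed rescue, and it leaves azathioprine as the named example directly before a mandatory-stop sentence that would not cover it. Sections 6.2.1 and 6.2.3 tell investigators in doubt to consult the medical monitor. That should reduce divergence between sites, but it does not say which rule prevails.

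Four stronger readings are tempting, and the documents do not support them.

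- **That steroid increases are caught in the same way.** Section 6.2 names them as escalation, but 6.2 and 6.2.3 both permit corticosteroid rescue. Part of the steroid text in 6.2.3 is blacked out, so the full rule cannot be read.
- **That the visit path is flatly contradictory.** No Table 6-2 row is both case by case and tied to the visit schedule. Footnotes 19 and 20 with Section 9.1.1 allow the schedule to mean the TD and follow-up visits.
- **That about 21 participants will be affected.** The cited trial's 12 flares in 120 would give 206 × 12/120 = 20.6. This counts all flares, including those managed with steroids, and the protocol's own expectation is below 10%.
- **That a participant stopping at Week 72 is followed to Week 84 or to Week 120, a 36-week difference.** This holds only if the visit schedule means all remaining treatment visits.

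The defence is also right that the longer path would not enlarge the adverse event counts: SAP 2.4 ends treatment-emergent events at last dose plus 98 days, or at end of study if earlier.

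**Conclusion.** The conflict holds for one drug class. New DMARD or immunosuppressant use for a flare is a mandatory stop on the natural reading of Section 6.2, and discretionary under 6.2.3, Table 6-2 and 9.1.1. This rests on reading the escape-treatment sentence as governing the escalation examples just before it. The visit path after stopping is a separate and softer problem: ambiguous, not contradictory.

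The number affected is some unknown part of a group that the protocol expects to be under about 21 of 206. The study is descriptive, so no test or power is at stake. The consequences are inconsistent handling of a safety-relevant combination, site-dependent exposure and completion counts, and uncertain placement of off-drug laboratory and vital-sign values. The overlapping windows depend on the EoP3 assumption stated above. The point merits correction but does not undermine the study.

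**What to change.** Reconcile Protocol 6.2, 6.2.3, Table 6-2, 9.1.1 and Table 8-1 footnote 19 so that they give:

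1. one discontinuation rule for new or changed DMARD or immunosuppressant use;
2. one stated visit path after discontinuation, saying explicitly whether treatment-period visits continue.

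The choice of clinical rule belongs to the sponsor's clinicians, and none is proposed here.

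In the SAP, align disposition with the reconciled rule, define EoP3 for participants who stop early, and state which window takes their later visits, including the window for Week 112.

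The cost is a protocol clarification or short amendment and a few lines in the SAP. If the visits have already taken place, the SAP can still state how post-discontinuation visits are classified.

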6.2.1 Concomitant therapy

All medications, procedures, and significant non-drug therapies (including physical therapy and blood transfusions) administered after the participant was enrolled into the study must be recorded on the appropriate Case Report Forms.

Each concomitant drug must be individually assessed against all exclusion criteria/prohibited medication. If in doubt, the Investigator should contact the Novartis medical monitor before re-assigning treatment for a participant or allowing a new medication to be started. If the participant is already enrolled, contact Novartis to determine if the participant should continue participation in the study.

Concomitant treatment may include standard of care for dry eye and dry mouth symptoms, such as the use of artificial tears and artificial saliva/salivary stimulants (e.g., cevimeline, pilocarpine) at the discretion of the treating physician. Amount and frequency of use should be recorded at each visit.

Short term use of oral analgesics (NSAIDs, paracetamol) is permitted. Azathioprine (up to 150 mg/day), methotrexate (≤ 25 mg/week) and hydroxychloroquine (≤ 400 mg/day) are allowed as stable background medication defined as continued treatment ≥ 3 months without dose adjustments. Steroids (prednisone or equivalent ≤ 10 mg/day) are allowed during the extension study and tapering is permitted at intervals not exceeding prednisone 2.5 mg/2 weeks.

Pre-emptive therapy with lamivudine or entecavir is allowed for participants with Hepatitis B surface antigen (HBsAg) seroreversion while on study treatment. Similarly, CMV antiviral medication used as pre-emptive therapy is allowed for participants with detectable virus by PCR.

Note: Background and concomitant medications will not be provided by Novartis and must be supplied by the study center.

6.2.2 Prohibited medication

Use of treatments displayed in the below table is not allowed in study periods as indicated.

Table 6-2 Prohibited medication

Medication	Prohibited in Study Period	Action to be taken
Other experimental therapies	All	Study treatment discontinuation required, participants should remain in the study and follow visit schedule
Other biologics (for treatment of autoimmune diseases e.g., SjS, SLE, RA)	All	Study treatment discontinuation required, participants should remain in study and follow visit schedule

Medication	Prohibited in Study Period	Action to be taken
DMARDs or other immune suppressive agents or changes in an existing DMARD regimen (hydroxychloroquine, methotrexate, azathioprine)	Treatment period	Study treatment discontinuation may be required on a case-by-case basis
Prednisone >10 mg (or equivalent other corticosteroid)	Treatment period	Study treatment discontinuation may be required on a case-by-case basis
Intravenous or oral cyclophosphamide; oral cyclosporine; oral MMF	All	Study treatment discontinuation required, participants should remain in the study and follow visit schedule
Existing co-medications observed to cause in an individual patient a major side effect of dry mouth/eyes. Examples include antihistamines, antidepressants, anticholinergics, sedatives, antipsychotic drugs, anti-Parkinson agents A comprehensive guide to medications with documented effects on salivary gland function or symptoms has been published by Wolff et al 2017 (please see the footnote).	Treatment period	Study treatment discontinuation may be required on a case-by-case basis
Live/attenuated vaccine	During treatment and for at least 14 weeks thereafter	Study treatment discontinuation required, participants should remain in the study and follow visit schedule

6.2.3 Rescue medication

There is no established, approved immunosuppressive treatment for SjS. Participants may receive NSAIDs, paracetamol, or symptomatic care at the discretion of the treating physician as outlined in [Section 6.2.1](#). Each concomitant drug must be individually assessed against all exclusion criteria and prohibited medication ([Table 6-2](#)). When in doubt the Investigator should contact the Novartis medical monitor before treatment reassignment or allowing a new medication to be started. If any of the medications listed in [Table 6-2](#) is deemed a necessary rescue therapy, the Investigator must follow the actions to be taken outlined in this table. Rescue treatment is to be provided by the study center or personal physician. Participants must be encouraged to continue the follow-up visits even when discontinued permanently from the study treatment.

Corticosteroids may be administered to participants for SjS clinical disease flares after enrollment into this study as determined necessary by the responsible Investigator. [REDACTED]

- the incremental daily steroid dose is > 2.5 mg/day prednisone or equivalent, or
- the increased daily steroid dose is administered > 2 days within a 4-week period.

6.3 Participant numbering, treatment assignment, randomization

6.3.1 Participant numbering

Each participant is identified in the study by a Participant Number (Participant No.) that is assigned when the participant is enrolled into core study, CCFZ533B2201, and is retained for the participant throughout his/her participation in the trial. This being an extension study, the Participant No. will remain the same as that of the core study; new participant numbers will not be assigned.

The Participant No. consists of the Centre Number (Centre No.) assigned by Novartis to the investigative site with a sequential participant number suffixed to it, so that each participant's participation is numbered uniquely across the entire database. During the extension study, each participant will be uniquely identified by a Participant No..

6.3.2 Treatment assignment, randomization

No re-randomization will be performed in this study. At Week 60 of the core study, all eligible and consenting participants from the core study will be enrolled via Interactive Response Technology (IRT) and will be re-assigned to one of the treatment arms (refer to [Section 6.1.3](#)). An IRT algorithm will be programmed to assign the participant to blinded treatment in the extension study using ESSDAI (Cohort 1 and Cohort 2) and ESSPRI (Cohort 2) scores from predefined time points in the TWINSS core study. ESSDAI and ESSPRI scores at predefined time points will be transferred to the extension study IRT database by the electronic clinical outcome assessment (eCOA) vendor after the Investigator or his/her delegate has confirmed this transfer in the core study (for details, refer to the IRT user guide). The IRT will assign a number to the participant, which will be used to link the participant to a treatment arm and will specify a unique medication number for the first package of study treatment to be dispensed to the participant.

- For participants rolling over from Cohort 1 in the TWINSS core study, the change in ESSDAI score between Week 4 and Week 48 will be used to determine if the participant responded to treatment in the core study. If an ESSDAI score is missing at Week 4 and/or Week 48, then Week 0 or Week 40 scores should be respectively used for the algorithm. A decrease of 3 points or more from Week 4 (or Week 0 if the ESSDAI score is missing at Week 4) will classify the participant as a treatment responder in Cohort 1.
- For participants rolling over from Cohort 2 in the TWINSS core study, a change in both ESSDAI and ESSPRI scores between Week 4 and Week 48 will be used to determine if the participant responded to treatment in the core study. If an ESSDAI or ESSPRI score is missing at Week 4 and/or Week 48, then Week 0 or Week 40 scores should be

respectively used for the algorithm. A decrease of 1 point or more in both the ESSDAI and ESSPRI scores from Week 4 (or Week 0 if the ESSDAI or ESSPRI score is missing at Week 4) will classify the participant as a treatment responder in Cohort 2.

6.4 Treatment blinding

This will be a double-blind treatment **until the final database lock of Core study**. Participants, Investigator, site staff, and persons performing the assessments will remain blinded to the identity of the treatment until the final database lock of the core study, using the following methods:

1. Treatment assignment data are kept strictly confidential until the time of unblinding and will not be accessible by anyone else involved in the study with the exception of the bioanalyst
2. The identity of the treatments will be concealed by the use of investigational treatments that are all identical in packaging, schedule of administration and appearance

The re-assignment codes associated with participants from whom PK samples are taken will only be disclosed to the PK bioanalysts who will keep the PK results confidential until primary database lock of the core study (Week 24). Blood samples for PK, immunogenicity and ██████████ assessment will be collected for all participants.

Whenever needed or requested by the clinical team, before the open-label part of the extension study, the bioanalyst will share bioanalytical data in a blinded fashion with the pharmacokineticist.

Up to final database lock of core study, unblinding will only occur in the case of subject emergencies (see [Section 6.6.2](#)).

After final database lock of core study, the treatment arm for individual participant will be unblinded and the study will be conducted open-label.

Unblinding of the CTT will occur at the time of the primary database lock at Week 24 for each cohort of the core study.

Table 6-3 Blinding and unblinding plan

Role	Time or Event				
	Treatment re-assignment list generated	Treatment allocation & dosing	Safety event (single participant unblinded)	Primary database lock at Week 24 of core study	Final database lock of core study
Participants	B	B	B	B	U
Site staff	B	B	UI	B	U
PK sample analyst(s)	B	U	UI	U	U
Global Clinical Supply and Randomization Office	U	U	U	U	U

Role	Time or Event				
	Treatment re-assignment list generated	Treatment allocation & dosing	Safety event (single participant unblinded)	Primary database lock at Week 24 of core study	Final database lock of core study
Unblinded Pharmacovigilance sponsor staff	B	UI	UI	UI	U
Data Monitoring Committee (DMC)	B	U	U	U	U
CTT and other sponsor teams (trial team, project team, management & decision boards, support functions)	B	B	B	U	U

Key:

UI: Allowed to be unblinded on individual participant level

U: Unblinded

B: Remains blinded

